4.11 Testing/Validation Plan

All statistical analyses will be programmed using SAS® software version 9.3, or later. Testing and validation plans for all programs will be developed in accordance with contract research organization guidelines and will include independent programming of tables and analyses.

5. DEFINITIONS

5.1 Abbreviations

Abbreviation	Definition
AE	Adverse Event
ANCOVA	Analysis of Covariance
ATC	Anatomical Therapeutic Chemical Classification System
CSR	Clinical Summary Report
ICH	International Conference on Harmonisation
MedDRA®	Medical Dictionary for Regulatory Activities
mL	Milliliter
NA	Not applicable
ng	Nanogram
NSAID	Non-steroidal anti-inflammatory drug
OA	Osteoarthritis
OAK	Osteoarthritis of the knee
OMERACT-OARSI	Outcome measures in rheumatology clinical trials and osteoarthritis research
PGA	Patient's global assessment of disease severity
PP	Per protocol population
SAE	Serious adverse event
SAS	Statistical Software from SAS Institute
SD	Standard deviation
SEM	Standard error of the mean

TEAE	Treatment-emergent adverse event
WO	Washout
WOMAC	Western Ontario and McMaster Universities Arthritis Index

5.2 Definitions

Adverse Event (AE)

An adverse event (AE) is defined as any undesired medical occurrence in a patient or clinical investigation patient receiving a pharmaceutical product and which does not necessarily have a causal relationship with this treatment. An AE can therefore be any unfavorable sign and unintended sign (including an abnormal laboratory finding comparing pre-treatment to post-treatment), symptom, or disease temporarily associated with the use of a study drug, whether or not related to the study drug.

AEs will be graded for severity using the following categories. Missing grade will be assigned a grade of 3 (severe) in tabulations.

Grade 1 (MILD): The symptom is barely noticeable to the study patient and does not influence performance or functioning. Concomitant medication is not ordinarily indicated for relief of mild AEs.

Grade 2 (MODERATE): The symptom is of sufficient severity to make the study patient uncomfortable and to influence performance of daily activities. Concomitant medication may be indicated for relief of moderate AEs.

Grade 3 (SEVERE): The symptom causes severe discomfort, sometimes of such severity that the study patient cannot continue in the study. Daily activities are significantly impaired or prevented by the symptom. Concomitant medication may be indicated for relief of severe AEs.

Relationship to study drug will be codes using the following categories. Missing relatedness will be assigned to “related” in tabulations.

Unrelated: The adverse event is unlikely to have been caused by study drug.

Possibly related: It is unclear whether the adverse event may have been caused by study drug.

Related: The adverse event is likely to have been caused by study drug.

Serious Adverse Event:

A serious adverse event (SAE) is defined as an adverse event that

- Results in death
- Is life-threatening (patient is at immediate risk of death from the event as it occurred)

- Requires in-patient hospitalization (formal admission to a hospital for medical reasons) or prolongation of existing hospitalization
- Results in persistent or significant disability/incapacity
- Results in a congenital anomaly/birth defect

Treatment-Emergent AE:

A treatment-emergent AE (TEAE) is any AE that begins or increases in severity after the initial dose of study drug.

Age

Subject's age is defined as its integer value in years at enrollment.

Baseline

For any variable, unless otherwise defined, baseline is the last assessment taken prior to the first study drug administration.

Change from Baseline:

The arithmetic difference between a post-baseline value and the baseline value:

Change from Baseline = (Post-baseline Value – Baseline Value)

Percentage Change from Baseline = [(Post-baseline Value – Baseline Value) / Baseline Value] x 100

End of Study

End of study is at Visit 17 (Day 280 ± 14 days), unless terminated early.

Enrollment date

Enrollment date is the same as the randomization date and is designated Day 0.

Study drug

Study drug in this study is Ampion or saline.

Randomization date

Randomization date is the day the subject is assigned a randomization number on study Day 0.

Study Day 0

Day 0 is defined as the first day that study drug is administered to the subject.

Study Day

Day of treatment: study day = (visit date - date of Study Day 0)

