10.3 ANALYSIS POPULATIONS

10.3.1 Safety Analysis Population:

The safety analysis population is defined as all subjects who are enrolled in the AP-003-C-OLE study and receive at least one dose of study medication (Ampion™). Subjects will be analyzed as treated.

10.3.2 Intent-to-treat Population:

The intent-to-treat (ITT) analysis population is defined as all subjects who are enrolled and receive at least one dose of study medication (Ampion™). Subjects will be analyzed as treated.

10.3.3 Per Protocol Population:

The per protocol analysis population is defined as all subjects included in the ITT analysis who met all entry criteria and had no major protocol violations as determined by the sponsor prior to analysis. All efficacy analyses will be repeated in the per-protocol population. These analyses will be supportive of the ITT analysis. Subjects will be analyzed as treated.

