10.3.6 Definition of Study Visits

This clinical trial has a total of 9 study visits, including telephone contacts, during the 40-week study (see Table 6.2). The time-on-study for each subject observation will be defined relative to Day 0 of the initial dose of the AP-003-C main study. For the proposed summaries of the data, several “baseline” measures will be utilized.

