10.3.10 Blinding and randomization

No blinding or randomization is required for the AP-003-C-OLE study. All subjects will receive Ampion™ 4-mL at each in-clinic visit.

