4.6 Blinding and randomization

This is an open-label study where all subjects will receive Ampion 4mL as an intra-articular injection in the study knee.

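### The start of the TEAE count is contradictory: SAP 5.2 ties it to a study drug defined as Ampion or saline and to a randomization that the extension does not have

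*SAP*

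**What the plan says.** The incidence and severity of TEAEs is the sole primary endpoint (protocol 3.5.1 and 10.4.1, SAP 3.1). SAP 5.2 defines it: "A treatment-emergent AE (TEAE) is any AE that begins or increases in severity after the initial dose of study drug". The study whose dose is meant is not named.

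The definitions that this sentence relies on follow in the same section:

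- Study drug: "Study drug in this study is Ampion or saline".
- Enrollment date is equated with the randomization date and called Day 0, and "Randomization date is the day the subject is assigned a randomization number on study Day 0".
- Day 0 is the first day on which study drug is given, again with no study named.
- "End of study is at Visit 17 (Day 280 ± 14 days), unless terminated early".

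Elsewhere the documents describe a different study. Protocol 10.3.10 states: "No blinding or randomization is required for the AP-003-C-OLE study". SAP 4.6 states: "This is an open-label study where all subjects will receive Ampion 4mL as an intra-articular injection in the study knee". Protocol 10.3.1 builds the safety population on receipt of Ampion alone.

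On the time origin, protocol 10.3.6 says: "The time-on-study for each subject observation will be defined relative to Day 0 of the initial dose of the AP-003-C main study". SAP 4.2 measures time from the first dose of the extension itself, and footnote 1 to protocol Table 6.1 labels the first extension injection Day 0.

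**The concern.** The definition of the only primary endpoint depends on two terms, study drug and Day 0. One of them names a treatment that nobody receives in this study. The other is tied to an event, randomization, that took place only in the main study. The protocol and SAP then give opposite time origins.

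The choice affects real records. Protocol 9.3 opens the AE reporting period at the main-study injection. Protocol 5.1.1 and footnote 7 to Table 6.1 have Visit 9 collect AEs still ongoing from the main study, and 5.1.1 adds new AEs before the injection. These passages separate events by timing but do not say whether the earlier ones are TEAEs. SAP 9.1 also imputes some partial or missing start dates to a first dose that it does not define. If that date and the TEAE origin were read differently, an event with no start date could be placed at main-study Day 0 and drop out of an extension count.

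At stake is the label on the primary table. Two programmers working from different sections could produce different rates, and one of those rates could include events that followed saline in a table presented as Ampion safety.

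**Working it through.** **1. The passages side by side**

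| Source | Origin it supports |
|---|---|
| SAP 4.2, time on study | First extension dose |
| SAP 5.2, end of study at Day 280 | First extension dose |
| Protocol Table 6.1, footnote 1 | First extension dose |
| Protocol 10.3.6, time on study | First main-study dose |
| SAP 5.2, enrollment date equals randomization date | Main study, the only place where randomization occurred |
| SAP 5.2, Day 0 as first study drug, with saline as study drug | Not stated; a main-study saline injection fits the words |
| Protocol 9.3, AE reporting period | Main-study injection, but as a collection window only |

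None of these rows mentions TEAEs. The SAP as a whole leans to the extension clock, but nothing in it overrides the other rows.

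The end of the window is also inconsistent. One sentence of SAP 4.7.4 stops AE follow-up twelve weeks after first dose. The next paragraph of the same section runs documentation to the end of the study, and protocol 10.3.11.4 follows subjects to Visit 17 or early termination.

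**2. Number of prior-saline subjects**

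The plan gives no figure to reproduce. Inputs are the 6:1 allocation (protocol 1.2), arms of 140 and 25 (SAP 2.4) and up to 161 subjects (protocol 10.3.7). Roll-over is assumed proportional.

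- 161 × 1/7 = 23.0
- 161 × 25/165 = 24.4

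For these subjects a main-study origin adds 84 days, plus up to 170 days of roll-over window, or up to 254 days before any Ampion. Extension follow-up is 280 days.

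**3. Scale of the saline contribution**

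The documents contain no main-study AE data. The KL 4 saline TEAE rate from earlier studies is used as a stand-in: r = 150/338 = 0.444 (protocol Table 1.5.4). Every variant below assumes that all saline-period events enter the count; A and C also assume independent periods.

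*A. Constant hazard.* Let r accrue over 12 or 20 weeks, so h = −ln(1 − r)/12 = 0.0489 or −ln(1 − r)/20 = 0.0293 per week. The 40-week extension incidence is then 85.9% or 69.1%. The gain from starting at the main study is [1 − exp(−h(12 + gap))] × exp(−40h).

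- No gap: 6.28 or 9.18 points. Times the prior-saline share (0.143 to 0.152): 0.9–1.4 points.
- Gap 170/7 = 24.3 weeks: 11.75 or 20.26 points. Saline part: 1.7–3.1 points.

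*B. Risk varies between subjects* (gamma frailty, variance 1). S(t) = 1/(1 + Lt), with L = (1/(1 − r) − 1)/12 or /20. The gain is S(40) − S(52 + gap).

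- No gap: 4.89 or 6.00 points. Saline part: 0.7–0.9.
- Full gap: 10.86 or 13.79 points. Saline part: 1.6–2.1.

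*C. Extension incidence p assumed at 20% to 60%, no roll-over gap.* Saline part = (23/161) × (1 − p) × 0.444.

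- p = 0.20: 5.1 points
- p = 0.60: 2.5 points
- Whole clock shift, using 145/326 for prior-Ampion subjects: 20% becomes 55.6% (35.6 points) and 60% becomes 77.8% (17.8 points)

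Across A to C the saline part runs from 0.7 to 5.1 points and the clock shift from about 5 to 36 points. Most of the clock shift comes from the longer window and not from saline.

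**The case against.** The strongest reply is that the SAP already fixes the clock. SAP 5.2 makes enrollment Day 0 and makes Day 0 the first day of study drug; enrollment in this study is Visit 9; SAP 4.2 refers expressly to this study's first dose; and Day 280 as the end of study only works on that clock. An AE with onset before Visit 9 would then be a TEAE only if it worsened after the injection.

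Much of this stands: the extension clock is the better-supported reading. It does not close the matter, because the enrollment sentence equates enrollment with randomization, which happened only in the main study. SAP 4.2 does not mention TEAEs, contradicts protocol 10.3.6, and leaves saline in the study-drug definition.

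The reply is also right that the route to saline is an inference. Protocol 10.3.6 governs time on study and says nothing of TEAEs. The closing paragraph of SAP 4.1, which applies the main-study baseline to statistics listed earlier (TEAE incidence among them), gives efficacy as its purpose. No passage plans to merge resolved main-study events into the extension dataset; only the reporting window in protocol 9.3 implies it. A reader might infer that the plan will count saline-period events as Ampion TEAEs. The documents do not support that; they only fail to exclude it.

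The reply is fair on size too. The 44% rate pools studies that differ in length and dosing, and the result follows largely from the extension incidence one assumes.

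**Conclusion.** The definition is wrong as written and should be corrected before the tables are programmed. SAP 5.2 names a treatment and a randomization that this extension does not have, and the protocol and SAP disagree on the time origin. The extension injection is the likelier intended start, but a literal reading lets a main-study saline injection start the count.

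The size cannot be determined from the documents. About 23–24 of 161 subjects would be prior-saline if roll-over is proportional. Saline-period events would add roughly 1–5 points of TEAE incidence, given the borrowed 44% rate, the assumed extension incidence and a merge of main-study AE data. A reader might infer a measured contamination of the primary endpoint from these figures; they show scale only, and the defect does not depend on them.

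The study is descriptive, so no hypothesis test or error rate is touched. The possible harm is a mislabelled primary rate.

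**What to change.** 1. SAP 5.2: define study drug as Ampion. Delete the saline wording and the randomization-date definition, including its use in the enrollment-date definition.
2. SAP 5.2: state that extension TEAEs are AEs that begin or worsen after the Visit 9 injection, through Visit 17 or early termination.
3. SAP 9.1: make the first dose used for date imputation that same date.
4. Protocol 10.3.6: align the time origin with SAP 4.2.
5. SAP 4.7.4: reconcile the twelve-week AE follow-up sentence with follow-up to Visit 17 in protocol 10.3.11.4.
6. Remove the remaining randomization references in SAP 4.7.2 and listing 16.1.

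Optional, to serve the objective of 52 weeks and/or five injections: one cumulative TEAE table from each subject's first Ampion dose (main-study Day 0 for prior-Ampion subjects, Visit 9 for prior-saline subjects), with main-study saline-period events listed separately.

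The cost is text edits in the SAP and one protocol section, plus one table and one listing if the option is taken. No new data collection is needed, since protocol 9.3 already sets the AE reporting period from the main-study injection.

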6. CHANGES FROM PROTOCOL-SPECIFIED ANALYSES

Modifications to the planned statistical analyses should be minimized. Nonetheless, the data obtained from the study may indicate that the planned analyses are inappropriate,

that additional analyses need to be performed, or that the design of the study needs to be modified, due to factors such as the distribution of the data or imbalance in important covariates. The study report will provide a detailed explanation for any deviations from the planned analyses.

7. LIST OF PLANNED TABLES, FIGURES, AND LISTINGS

Tables are categorized and numbered in accordance with ICH E3 guidelines. Each table, figure and listing is presented by treatment arm. All efficacy tables will be provided both for ITT and PP. Accountability tables will also include an overall column. Listings will be sorted by treatment, subject ID, and by visit, if multiple visits exist. These will be provided in a separate document.

Number	Title
14.1 Accountability	
14.1.1	Accountability (Analysis Population: All Enrolled)
14.1.2	Enrollment by Site (Analysis Population: All Enrolled)
14.1.3	Analysis Populations (include ITT, safety, PP, and reasons for PP exclusion)
14.1.4	Subject Disposition (all screened)
14.1.5	Major Protocol Deviations (Analysis Population: All Enrolled)
14.1.6.1	Demographics and Baseline Characteristics (Analysis Population: ITT)
14.1.6.2	Demographics and Baseline Characteristics (Analysis Population: PP)
14.2 Efficacy	
14.2.1.1	Summary of OMERACT-OARSI Percent Responder Status (Analysis Population: ITT)
14.2.1.2	Summary of OMERACT-OARSI “controlled” responders (WOMAC A and C)
14.2.1.3	Summary of responders demonstrating a 20% improvement and 0.5 shift in PGA
14.2.1.5	Summary of Patients responding to 50% improvement in Pain and 1.0 absolute change
14.2.1.6	Summary of Patients responding to a 50% improvement in Function and 1.0 absolute change
14.2.1.7	Summary of Patients responding to a 20% improvement in Pain and 0.5 absolute change
14.2.1.8	Summary of Patients responding to a 20% improvement in Function and 0.5 absolute change
14.2.1.9	Summary of Patients responding to a 20% improvement in PGA and 0.5 absolute change
14.2.1.10	Summary of WOMAC A mean change
14.2.1.11	Summary of WOMAC A percent change
14.2.1.12	Summary of WOMAC B mean change
14.2.1.13	Summary of WOMAC B percent change
14.2.1.14	Summary of WOMAC C mean change
14.2.1.15	Summary of WOMAC C percent change
14.2.1.16	Summary of WOMAC A and C mean change
14.2.1.17	Summary of WOMAC A and C percent change
14.2.1.18	Summary of PGA mean change
14.2.1.19	Summary of PGA percent change
14.2.1.20	Summary of WOMAC mean change
14.2.1.21	Summary of WOMAC percent change

Number	Title

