6.1.2 Patient's Global Assessment of Disease Severity (PGA)

The PGA should be completed by subjects at each in-clinic visit (prior to injection).

Subjects are asked the following question: “Considering all the ways in which your arthritis affects you, please indicate how you are doing.”

Subjects respond by using a 5-point adjectival Likert score (0 = very well, 1 = well, 2 = fair, 3 = poor, 4 = very poor).

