- Change in contralateral knee pain (WOMAC A) between Visit 9 and Visit 17
- Change in contralateral knee stiffness (WOMAC B) between Visit 9 and Visit 17
- Change in contralateral knee function (WOMAC C) between Visit 9 and Visit 17
- Time to Total Knee Replacement (TKR)
- Use of rescue analgesia (amount of acetaminophen used)

Exploratory efficacy analyses include the mean change and percent change in WOMAC A, WOMAC B, WOMAC C, WOMAC A1-2, WOMAC A3-5, PGA and amount of acetaminophen used from Visit 1 to Visit 17 using an analysis of covariance model, adjusted for baseline value.

Percent responders using the OMERACT-OARSI responder criteria will be analyzed defined as the percent of subjects whom respond to treatment from Visit 1 to Visit 17. Interim visits will also be analyzed.

1. High improvement in pain or in function $\geq 50\%$ and absolute change in Likert pain scale of ≥ 1 OR
2. Improvement in at least two of the 3 following:
 - a. pain $\geq 20\%$ and absolute change in Likert score ≥ 0.5
 - b. function $\geq 20\%$ and absolute change in Likert score ≥ 0.5
 - c. subject's global assessment $\geq 20\%$ and absolute change in Likert score ≥ 0.5

All of the above endpoints will be evaluated via descriptive statistics and confidence intervals.

The WOMAC Pain Score, the WOMAC Function Score, then PGA score and the OMERACT-OARSI responder criteria, will be analyzed via a repeated measures analysis of variance to determine if there is a significant time effect for these endpoints. Also, to aid in the interpretation of these results, a stability analysis will be performed on these same endpoints. That is, mean pairwise differences between administration time points will be calculated along with their 95% confidence intervals. If stability is achieved at some time point, then the following mean differences should be not be different from zero, in that the confidence interval should include zero.

Adverse events will be tabulated for both number of subjects and number of events by subject and overall study population, summarized by any event, body system, and preferred term. Summaries by serious, severity, and relationship will also be done.

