4. HYPOTHESES AND METHODS

4.1 Primary Analysis Methodologies

Since this is an observational study on the repeat administration of Ampion 4 mL injection, no formal hypotheses will be tested in this study. There will be no comparisons made to threshold values or to “historical” control values. There is no comparator in this study.

All analyses will be descriptive in nature and will be performed at each efficacy assessment (Visit 9 (Enrollment), Visit 11 (Week 12), Visit 13 (Week 24), Visit 15 (Week 36) and Visit 17 (Week 40)). For dichotomous outcomes, the percentage of patients with that outcome will be estimated and exact 95% binomial confidence intervals will be calculated. These dichotomous outcomes are:

- The incidence of treatment emergent adverse events
- Responder status based on the OMERACT-OARSI responder criteria
- Evaluate OMERACT-OARSI ‘controlled’ responder defined as a 20% improvement in Pain and Function and 0.5 point absolute change in the 5-point Likert Scale
- Evaluate 20% improvement in PGA and 0.5 point absolute change in the 5-point Likert Scale

The outcomes with more continuous responses will be analyzed via descriptive statistics (n, mean, standard deviation, median, minimum, and maximum). Also, 95% confidence intervals from the mean response will be calculated. These outcomes are:

- Mean change and percent change in WOMAC A pain subscore
- Mean change and percent change in WOMAC B stiffness subscore
- Mean change and percent change in WOMAC C physical function subscore
- Mean change and percent change in PGA
- Mean Change and percent change in WOMAC A pain subscore questions 1 and 2 (pain with movement)
- Mean Change and percent change in WOMAC A pain subscore questions 3–5 (resting pain)
- Change in contralateral knee pain (WOMAC A)
- Change in contralateral knee stiffness (WOMAC B)
- Change in contralateral knee function (WOMAC C)

Differences in pain scores between successive visits will be estimated via descriptive statistics and confidence intervals.

The time to total knee replacement will be summarized using Kaplan-Meier methodologies. The use of rescue analgesia will be summarized as the dichotomous outcome on the number of patients using rescue medication and as continuous variables on the number of medications use.

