4.10 Outliers

No formal outlier tests are planned. Values that are outside the pre-defined range, such as a WOMAC score not between zero and four, or a PGA score not between one and five, would be queried and excluded if necessary prior to database lock.

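### On a single-item 0–4 PGA the 20% and 0.5-point responder thresholds filter nothing: the endpoint is improvement by at least one category, tabulated twice and without the worsening share beside it

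*SAP*

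**What the plan says.** Protocol 6.1.2 defines the PGA as one question, "Considering all the ways in which your arthritis affects you, please indicate how you are doing", answered on a "5-point adjectival Likert score (0 = very well, 1 = well, 2 = fair, 3 = poor, 4 = very poor") scale. Each visit gives one whole number, and lower is better.

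SAP 4.1 lists the dichotomous PGA outcome as "Evaluate 20% improvement in PGA and 0.5 point absolute change in the 5-point Likert Scale". It is to be reported as a percentage with an exact 95% binomial interval. SAP 4.1 also says that there is no comparator, no threshold and no hypothesis test, and it asks for the same statistics from the main-study baseline. Protocol 10.4.2 gives the inequality for the absolute part ("absolute change in Likert score ≥ 0.5") and uses the same PGA component as item 2c of the OMERACT-OARSI definition.

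SAP section 7 lists two tables for this criterion: 14.2.1.3, "Summary of responders demonstrating a 20% improvement and 0.5 shift in PGA", and 14.2.1.9, "Summary of Patients responding to a 20% improvement in PGA and 0.5 absolute change". No table title mentions worsening.

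SAP 4.10 uses a different range. It says that "a PGA score not between one and five, would be queried and excluded if necessary prior to database lock".

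**The concern.** A stated rule of 20% and 0.5 point reads as a filter that removes trivial movement. On a single integer item nothing lies below the filter except no change or worsening. A reader of Table 14.2.1.3 would credit the PGA responder rate with a stringency that it does not have.

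This matters more in a one-arm study. Ordinary visit-to-visit movement goes both ways, but a responder percentage counts only the favourable direction, and there is no control arm to show how much of it is background. Setting the worsening share beside the improving share is the simplest substitute, and no listed table title provides for it.

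**Working it through.** **Inputs from the documents.** PGA values 0, 1, 2, 3, 4 (Protocol 6.1.2). Rule: relative improvement ≥ 20% and absolute improvement ≥ 0.5 (Protocol 10.4.2; SAP 4.1 gives no sign). Percentage change = (post − baseline) / baseline × 100 (SAP 5.2). The plan states no expected PGA responder rate, SD or reliability, so there is no figure to reproduce.

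**Step 1: does either threshold bind on 0–4?** One-category steps:

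| From → to | Absolute | Relative |
|---|---|---|
| 4 → 3 | 1 | 1/4 = 25% |
| 3 → 2 | 1 | 1/3 = 33% |
| 2 → 1 | 1 | 1/2 = 50% |
| 1 → 0 | 1 | 1/1 = 100% |

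Larger steps have larger values on both measures. All 4 + 3 + 2 + 1 = 10 possible improvements pass both parts. At baseline 0 no improvement is possible. The rule is therefore identical to improvement by at least one category.

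**Step 2: contrast with pain.** WOMAC A scored as the mean of five items moves in steps of 0.2, which gives 210 possible improvements. Of these, 39 are below 0.5 point (20 of size 0.2 and 19 of size 0.4), and 14 of the 39 still reach 20%. A further 5 reach 0.5 point but not 20% (0.6 point from a baseline of 3.2 to 4.0). So 39 + 5 = 44 of 210 fail at least one part. The same wording is a real filter for pain and none for PGA.

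**Step 3: the one-to-five coding in SAP 4.10.** All 10 improvements still pass with ≥, but 5 → 4 is 1/5, exactly 20%, and would fail if programmed as > 20%. Conversely, if the data are coded 0–4, a valid score of 0 falls outside the SAP's range check.

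**Step 4: how much one-directional movement could there be?** Assumptions, none from the documents: a latent normal score with the same mean (2.0 to 2.5) and SD (0.7 to 1.1) at both visits and correlation r between visits, rounded to 0–4.

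| Assumed r | Improve ≥ 1 category | Worsen ≥ 1 category |
|---|---|---|
| 0.5 | 25% to 32% | same |
| 0.7 | 21% to 28% | same |
| 0.8 | 17% to 24% | same |
| 0.9 | 12% to 18% | same |

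At r = 0.95 and SD 0.7 to 1.0 the share falls to 9% to 12%; at 0.99, to 4% to 5%. From the main-study baseline, where subjects were selected on WOMAC pain of at least 1.5, regression to the mean can tilt the split. With PGA SD 0.85, pain–PGA correlation 0.4 to 0.6 and r 0.5 to 0.9 (all assumed), 16% to 34% improve and 14% to 25% worsen.

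**Step 5: what the added display would show.** Take 136 subjects (Protocol 10.3.7; SAP 2.4 gives 100 and SAP 4.3 about 160) and suppose that 34 improve, 34 worsen and 68 are unchanged. The planned output is 34/136 = 25%, exact 95% CI 18.0% to 33.1%. The net difference is (34 − 34)/136 = 0. Its standard error is √[(34 + 34) − (34 − 34)²/136] / 136 = 8.25/136 = 6.1 points, so the 95% CI is −11.9 to +11.9 points. The two results answer different questions, and only the first is planned.

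**The case against.** The best defence is that little hangs on this endpoint. It is one of 14 exploratory items and the primary endpoint is TEAEs. Nothing is tested, so no error rate, sample size or decision is affected. That stands.

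Nor is net direction missing from the plan. Mean PGA change with a 95% CI is planned at each efficacy visit (SAP 4.1; Tables 14.2.1.18 and 14.2.1.19), and Protocol 10.4.2 adds repeated-measures and stability analyses of PGA. With equal improving and worsening shares the mean change would sit near zero. This stands too, although it does not put the worsening share beside the responder rate. The table shells are not available here, so the absence of a worsening row is inferred from titles.

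A reader might go further in three ways that the documents do not support:

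- **That a large responder rate is expected with no change at all.** If no score moves, the rate is exactly 0%. The claim needs within-subject fluctuation around an unchanged mean, and its size depends on a reliability that the documents do not give.
- **That an interval excluding zero would be misleading evidence of effect.** An exact interval has a lower limit above zero whenever there is at least one responder, and no comparison with zero is planned for this proportion.
- **That the PGA item inflates the OMERACT-OARSI composite.** Item 2c cannot make a responder alone; pain or function must also qualify. Any effect on the composite has not been quantified.

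Finally, the rule could bind on unrounded multiple-imputation values, which SAP 4.8 allows as an alternative. The equivalence holds for observed, worst-observation and last-observation values.

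**Conclusion.** The point holds as one of labelling and interpretation. For observed or carried-forward integer scores on the protocol's 0–4 scale, the PGA responder endpoint is exactly improvement by at least one category, and Tables 14.2.1.3 and 14.2.1.9 report it twice. This part is arithmetic and needs no assumption beyond the 0–4 coding; on a 1–5 coding it needs the inclusive inequality.

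Without a comparator, the percentage cannot be separated from one-directional fluctuation. The illustrative 12% to 32%, with an equal share worsening, rests entirely on assumed reliability of 0.5 to 0.9, an assumed spread and no mean change. It is not a prediction for this trial, and a more stable instrument would give less.

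**What to change.** 1. Define PGA response in SAP 4.1 and in the table title as improvement of at least one category.
2. Keep one of Tables 14.2.1.3 and 14.2.1.9. Use the other for improved, unchanged and worsened by at least one category, by visit and for each baseline (Visit 9 and main-study Day 0), with the net difference (improved minus worsened) and a paired 95% CI. If the component series 14.2.1.5 to 14.2.1.9 is to stay intact, replace 14.2.1.3.
3. Reconcile the PGA range in SAP 4.10 with Protocol 6.1.2, and write both inequalities as ≥.

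The cost is SAP wording and the re-use of a table already planned; no new data are needed. The downside for the sponsor is that the PGA responder rate will look less favourable beside the worsening rate. A stricter cut, such as two categories, is a matter of preference and is not needed to settle this point.
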